## **6. PHARMACEUTICAL INFORMATION**

### **6.1 Study Agent (IND #59,081, BHR Pharma, LLC)**

**Structures of Tamoxifen [as (Z) isomer], 4-OHT [as (Z) isomer], and the Primary Metabolites of 4-OHT**

[figure not shown]

Figure 2. Tamoxifen and its metabolites. (A) chemical structures [as Z isomer] and metabolism [Jin Y, JNCI 2005 p30-39] (B) rapid conversion between two isomers of 4-OHT by light exposure (non-enzymatic) leads to equilibrium.

Table 1: Composition of 4-OHT Gel [0.228% 4-OHT (w/w) ] Formulation for present study

Ingredient	Quantity per 100 g gel
4-OHT	0.228 g
95% ethyl alcohol, EP	72 g
Isopropyl myristate, EP	1 g
Hydroxypropylcellulose, EP	1.5 g
Phosphate buffer ¼ (v/v), pH 7, consisting of:	26.372 g
Potassium dihydrogen phosphate( $\text{KH}_2\text{PO}_4$ )	0.023 g
Disodium monohydrogen phosphate ( $\text{Na}_2\text{HPO}_4 \cdot 12\text{H}_2\text{O}$ )	0.092 g

4-OHT is produced by a step-wise synthetic process from the commercially-available raw materials anisole, 2-phenylbutyric acid chloride, 4-bromophenol, and 2-dimethylaminoethyl chloride: HCl. The crude 4-OHT is purified by recrystallization from methanol, resulting in two geometric isomer forms, E and Z. The drug substance is tested for identity, content, isomer ratio and purity prior to formulation into a hydroalcoholic gel product.

The agent to be supplied by the NCI, DCP Repository for this study, is based on the Besins Healthcare gel formulation containing 0.228 g of 4-OHT per 100 g of gel [0.228% on a weight-to-weight (w/w) basis] or 200 mg of 4-OHT in 100 mL of gel [0.2% on a w/v basis]

Chemically, tamoxifen is the trans-isomer of a triphenylethylene derivative. The chemical name is (Z) 2-[4-(1,2-diphenyl-1-butenyl) phenoxy]-N, N-dimethylethanamine 2-hydroxy-1,2,3- propanetricarboxylate (1:1).

Tamoxifen (20 mg) will be incorporated into opaque gelatin capsules and filled with microcrystalline cellulose powder.

Placebo capsules will be manufactured by incorporating only microcrystalline cellulose powder into identical opaque capsules.

## 6.2 Reported Adverse Events and Potential Risks

The toxicokinetics of 4-OHT have been investigated in seven studies in rats and dogs, treated with

repeated doses administered by subcutaneous or dermal routes. In general, plasma concentrations of 4-OHT increased in a dose-dependent manner following subcutaneous and dermal administration in rats and dogs. The intravenous and dermal administrations of 4-OHT were well tolerated by rats.

Repeated dermal doses of up to 1000 µg/kg/day of 4-OHT were administered to female rats. Repeated subcutaneous doses of up to 200 µg/kg/day of 4-OHT were administered to female rats and repeated subcutaneous doses of up to 150 µg/kg/day of 4-OHT were administered to female dogs. Dermal and subcutaneous doses of up to 200 µg/kg/day were generally well tolerated by rats, while subcutaneous doses of up to 150 µg/kg/day were shown to be well tolerated in dogs. There were no clinical signs of toxicity. However, decrease in body weight, reduced uterus and ovary size, and changes in the genital tract were observed.

The reproductive toxicity of 4-OHT was evaluated in 7 studies with rats and 3 studies with rabbits. Repeated doses of up to 200 µg/kg/day of dermal or subcutaneous administration of 4-OHT were well tolerated by rats and rabbits. When 4-OHT was cutaneously applied before mating until day 6 of pregnancy, impaired female fertility and retardation in fetal body weight were observed, but these effects were reversible when females were mated after a 14-day treatment-free period. Topical doses of up to 50 µg/kg/d in rats and 100 µg/kg/d in rabbits during organogenesis resulted in no embryotoxicity. Higher doses during organogenesis reduced body weight gain and increased the incidence of resorptions, and the highest dose of 200 µg/kg/d induced wavy ribs in some fetuses. Subcutaneous injection of 4-OHT at 20 µg/kg/d to F0 female rats following implantation to weaning of the progeny resulted in a reduced number of pregnant F0 females, a reduced number of delivered pups, and pups surviving the early post-partum. However, the physical and behavioral development of the F1 generation and its fertility were not affected at any dose.

The carcinogenic toxicity of 4-OHT was evaluated in one study in female rats. 4-OHT was not carcinogenic in rats treated with up to 1000 µg/kg/day topically for 101 weeks. Notably, during the carcinogenicity study, reduced incidence in mammary tumors was observed in treated rats, leading to lower mortality in treated rats.

4-OHT is the most active metabolite of the well-characterized antiestrogen compound, tamoxifen, which has been used in the treatment of estrogen receptor (ER) positive breast cancer for over 25 years. Tamoxifen was approved in 1998 by the FDA for prevention of breast cancer in high-risk women on the basis of a large, randomized, placebo-controlled study sponsored by the National Cancer Institute, which demonstrated a 50-percent reduction in the risk of ER positive breast cancers in women treated with tamoxifen (Fisher et al. 1998). Although its efficacy is well established in the treatment and prevention of certain breast cancers, tamoxifen increases the risk of several serious adverse events, particularly when used for several years. The most serious adverse events include endometrial cancer, deep-vein thrombosis, pulmonary embolism, stroke, and cataracts. However, thromboembolic events are not expected with transdermal 4-OHT use given the lack of first-pass hepatic metabolism.

Clinically significant adverse effects of topical 4-OHT have not been reported to date at the doses that have been studied (0.25 mg/day, 0.5 mg/day, 1 mg/day, 2 mg/day, and 4 mg/day).

Topical application of 4-OHT avoids first pass metabolism in the liver. Thus, the antiestrogenic activity of 4-OHT after percutaneous administration is expressed locally. Preliminary data from the studies described below indicate that 4-OHT at 1 mg/day and 2 mg/day has similar anti-proliferative activity in breast tissue as oral tamoxifen at 20 mg/day, with much lower plasma levels of 4-OHT. These plasma levels (50 and 130 pg/mL, respectively) are approximately 1/30 – 1/12 of those achieved after oral administration of standard doses (20 mg) of tamoxifen.

### **6.3 Availability**

6.3.1 Oral tamoxifen (20mg) capsules and matching placebo capsules are supplied by NCI, DCP Repository. Capsules will be packaged into bottles containing 120 capsules.

6.3.2 4-OHT and matching placebo gel are supplied by the BHR Pharma and distributed by NCI, DCP Repository (see Section 12.7). Each gel canister contains at least 80 reliable doses and will be metered to dispense 1mL per actuation, 2mg of 4-OHT gel per actuation (~40 days of therapy). Placebo canisters will contain an equal weight of placebo gel.

6.3.3 Agent will be supplied in a kit. Each kit contains two canisters of 4-OHT/ placebo gel and one bottle of 120 tamoxifen/placebo capsules. The kit will be given/shipped to the patient at the time of randomization and collected at Study Visit 1.

### **6.4 Agent Distribution**

Agents will only be released by NCI, DCP after documentation of IRB approval of the DCP-approved protocol and consent is provided to DCP and the collection of all Essential Documents is complete (see DCP website for description of Essential Documents).

NCI, DCP-supplied agents may be requested by the Investigator (or their authorized designees) at each Organization. DCP guidelines require that the agent be shipped directly to the institution or site where the agent will be prepared and administered. DCP does not permit the transfer of agents between institutions (unless prior approval from DCP is obtained). DCP does not automatically ship agents; the site must make a request. Agents are requested by completing the DCP Clinical Drug Request form (NIH-986) (to include complete shipping contact information) and faxing or mailing the form to the DCP agent repository contractor:

[name]  
MRIGlobal  
DCP Repository  
[name]  
[name]  
[contact]  
[contact]  
Emergency [contact]

### **6.5 Agent Accountability**

The Investigator, or a responsible party designated by the Investigator, must maintain a careful record of the inventory and disposition of all agents received from DCP using the NCI Drug Accountability Record Form (DARF). The Investigator is required to maintain adequate records of receipt, dispensing and final disposition of study agent. This responsibility has been delegated to the Research Pharmacist at each site, who will maintain receipt records detailing from whom the agent was received and to whom study agent was shipped, date, quantity and batch or lot number. On the dispensing record, quantities and dates study agent was dispensed to and returned by each participant will be noted.

### **6.6 Packaging and Labeling**

4-OHT and matching placebo gel are packaged by the BHR Pharma and distributed by the NCI, DCP Repository. Oral tamoxifen and matching placebo will be packaged by NCI, DCP Repository. Kits will be assembled by the NCI, DCP Repository.

The tamoxifen and placebo capsules will be packaged as 20 mg, or placebo capsules, in bottles of 120 capsules. Each bottle will have a label printed with the treatment kit number, protocol number, number of capsules, expiration date, and “tamoxifen citrate 20mg or placebo”.

Transdermal 4-OHT/ placebo gel is packaged in a container-closure system which consists of a pouch in a canister, a 1 mL pump, and a protective cap that covers the pump. The pouch contains 88g of gel. A single actuation delivers 1mL of gel with a 4-OHT concentration of 2mg/mL. Each canister will have a label printed with the treatment kit number, concentration and weight of gel, expiration date, protocol number and “4-Hydroxytamoxifen 2mg/mL or Placebo Gel ” along with the statement “Caution: New Drug- Limited by Federal law (US) to investigational use”. Each canister is packaged in a carton with the sample label. Detailed instruction for gel application will be provided.

Agent will be supplied in a kit. Each kit contains two canisters of 4-OHT/ placebo gel and one bottle of 120 tamoxifen/placebo capsules. Each kit will have a label printed with the treatment kit number, protocol number and contents and storage temperature along with the statement “Caution: New Drug- Limited by Federal law (US) to investigational use”. Each kit (and its contents) will be labelled so that any oral active kit or any gel active kit can be given to any participant. The portion of the label indicating placebo or active drug will be removed by the pharmacy when the kit is dispensed. The pharmacy will attach pre-printed label overlays with the randomization number of the subject receiving the study drug, and canisters numbers provided by MRI Global. Dispensing pharmacist shall open the kit, affix prescription labels to both capsule bottles and dispensers with written direction according to the prescribing instruction. Fill out blank sections on the bottles and dispensers indicating subject number and subject initials. Weigh all dispensers and record final gross weight on the space provided on the dispenser itself and on the form. Detach peel-off label from each kit and affix it to the form, which is kept in the study binder. Pharmacies that use an eDARF shall print out the logs from their electronic accountability system upon request and keep the logs in the study binder.

The kit will be given/shipped to the patient at the time of randomization and collected at Study Visit 1. If the kit is shipped to participant, the pharmacy or coordinator will package the supplies at controlled room temperature. Please see the NWU2015-06-04 pharmacy manual for shipping procedures and specifications.

Placebo gel will be packaged into canisters for the purpose of demonstration. These canisters are labeled “For demonstration purposes only” and provided to study coordinators to show consented participants how to pump the canister and what the gel looks like. Participants are allowed to touch the gel and are asked to wash their hands after the demonstration.

## **6.7 Storage**

All study drug must be stored in a secure limited-access area, at controlled room temperature ((20 – 25° C [68° to 77°F]); excursions are permitted to 15° to 30°C [59° to 86°F]) in accordance with labeled storage requirements. Each site’s supply of study drugs and placebos will be stored at their respective investigational pharmacies. Subjects will be instructed to store the study drug at home at room temperature, and to avoid extreme heat or cold during transportation from clinic to home. Investigational labeling will include instructions to keep the product out of reach of children.

## **6.8 Registration/Randomization**

1. A study coordinator must upload into the Northwestern Clinical Trials Management System, a signed and complete informed consent along with HIPAA authorization and a completed eligibility form for each participant identified as eligible to be entered into the study.
2. All participants must be registered in the Northwestern University Robert H. Lurie Comprehensive Cancer Center Clinical Trials Management System (CTMS). Participants must not start protocol treatment prior to registration in the Lurie Cancer Center CTMS.
3. After registration in the CTMS, participants will be assigned a participant identification number and a randomization number when applicable.
4. An NCPC Quality Assurance Monitor will submit the following into the REDCap Randomization Information Form: (1) Study Number, (2) Site, (3) Pharmacist Email(s), (4) Participant ID [PID], (5) Participant Initials, and (6) Randomization Date.
5. An Automatic Treatment Assignment Notification email will be sent to the research pharmacist(s) containing: (1) Study Number, (2) Site, (3) Participant ID [PID], (4) Participant Initials, (5) Randomization Date, and (6) Treatment Assignment.
6. The clinical research coordinator(s) will receive a Confirmation of Registration containing the PID via email.
7. The following people will have a copy of the un-blinded randomization log: the study statistician at NU, the Quality Assurance Team at NU, and the Investigational Pharmacists at each site. The following people will have access to the REDCap study project containing randomization information: the study statistician at NU and the Quality Assurance Team at NU. The study statistician will set up randomization blocks.

When possible, the study coordinator will notify an NCPC Quality Assurance Monitor and/or send an email to [[contact]](mailto:[contact]) prior to registering a participant. Prior notification is required for participant randomizations outside the normal business hours of Monday-Friday 9:00am-5:00pm CT.

## **6.9 Blinding and Unblinding Methods**

Study participants will receive a prescription, blinded, from the investigational pharmacy. The blind will be maintained through the effort of the research pharmacist and the pharmacy. Unblinding will only occur when it is deemed medically necessary, and will only take place after consultation with the PI and the NCI, DCP Medical Monitor:

Name: [name]  
Address: Division of Cancer Prevention  
National Cancer Institute  
[name]  
[name]  
[contact] (during normal business hours)  
[contact]  
[contact]  
Email: [[contact]](mailto:[contact])

After hours consultation will be provided by [name], at [contact] or [contact].

## **6.10 Agent Destruction/Disposal**

Tamoxifen capsules and 4-OHT gel: at the completion of investigation, all unused study agent will be returned to NCI, DCP Repository according to the DCP “Guidelines for AGENT RETURNS” and using

the DCP form “Return Drug List”, as specified in The Guidelines and form are available on the DCP website.

## 7. CLINICAL EVALUATIONS AND PROCEDURES

### 7.1 Schedule of Events

7.1.1 Expected duration of participation in the study: The interval from registration to the start of the intervention period will be a maximum of two weeks; the interval from Visit 1 (day of surgery) to Visit 2 is 1-21 days; and the (potential) interval from Visit 2 to the final phone call is up to 35 days. With an intervention period of 4 to 10 weeks, the minimum duration of participation is 29 days, and the maximum duration is 20 weeks.

### SCHEDULE OF EVENTS

Evaluation/ Procedure	Registration/ Screen 1	Randomization 	Study visit 1 (day of surgery) 	Study visit 2 (within 21 days after surgery)
Informed Consent	X			
Assess Eligibility	X			
Medical History	X		X 	
Physical Exam	X		X 	X
Vitals 	X		X	X
Breast Cup Size	X			
Blood draw for CBC and chemistry profile	X		X	
Research blood draw	X 		X 	
Pregnancy test 	X		X	
Menstrual period date 	X		X	X
BESS questionnaire 	X		X 	
Concomitant Medications	X		X 	
Dispense Study Agent		X		
Collect Study Agent			X 	
Review Agent Diary/Record		X	X 	
Adverse Events			X 	X
Fresh breast sample collection			X	
Record location & depth of lesion in breast			X	
Request paraffin blocks of core biopsy & surgery 		X (core biopsy)		X (surgical)
Assemble samples & mail to NU PCF				X
Phone calls timed from day 1 of intervention (up to 4 total) 		Weeks 1, 4  , 8 		0-5 weeks after Study Visit 2 

1. ECOG performance status, height, weight, blood pressure, pulse, and temperature
2. Research blood at Baseline (Screen 1) includes:
  - Two 2.7mL blue top tubes (Citrate) to obtain plasma for Coagulation panel assays.
  - Two 10 mL lavender top tubes (K2EDTA) to obtain plasma and buffy coat (WBCs for DNA/RNA isolation). Plasma will be obtained for 1) IGF-1, IGFBP-3, and SHBG assays; 2) steroid hormone assays (estradiol, progesterone). Buffy coat will be collected for future assessment of CYP2D6 polymorphisms in tamoxifen metabolism (refer section 10.2 for details).
3. Pregnancy tests will be performed on all women with child-bearing potential.
4. Record last and estimated next menstrual period at the Screen 1 visit. Confirm and record actual menstrual period date by a phone call to participant 1 week after the estimated date. Record last and estimated next menstrual period date at Visit 1. Confirm and record actual menstrual period date at Visit 2 or the final phone call.
5. Participants must be randomized within 90 days of DCNB and must start drug within 5 days after randomization.
6. Surgery must be scheduled to occur between 4-10 weeks after the patient begins the study agent. However, surgery date may be extended for 10 days beyond 10 weeks if required due to scheduling exigencies driven by patient's personal or health safety needs, surgeon's needs, or operating room schedule.
7. Source document will be anesthesiologist or surgeon pre-op history and physical. May have been performed on day of surgery or within 14 days prior.
8. Research blood on the Day of Surgery (Study Visit 1) includes: plasma for drug measurement (tamoxifen, N-desmethyltamoxifen, Z and E isomers of both 4-OHT and endoxifen) and for Coagulation panel assay (Factor VIII, von Willebrand Factor, Factor IX, and total protein S), and for IGF-1, IGFBP-3, and SHBG assays. WBCs will be used for extraction of DNA/RNA.
  - Two 2.7mL blue top tubes (Citrate) to obtain plasma for Coagulation panel assays.
  - Two 10 mL lavender top tubes (K2EDTA) to obtain plasma and buffy coat (WBCs for DNA/RNA isolation). Plasma will be obtained for 1) measuring tamoxifen and its metabolites [tamoxifen, N-desmethyl tamoxifen, (E) 4-OHT, (Z) 4-OHT, (E) endoxifen, and (Z) endoxifen]; 2) IGF-1, IGFBP-3, and SHBG assays; 3) steroid hormone assays (estradiol, progesterone). Buffy coat will be collected for future assessment of CYP2D6 polymorphisms in tamoxifen metabolism (refer section 10.2 for details).
9. For phone calls at weeks 1, 4, 8, a window of  $\pm 3$  days is allowed.
10. Questionnaires may be administered via interview or self-administered.
11. Institutions that do not allow release of paraffin blocks, will provide sections of the paraffin block as detailed in Section 10.2.3.
12. Visit 1 BESS questionnaire, collection of study agent, review of agent diary/record, review of concomitant medication, and review of adverse events may be performed at either Visit 1 (day of surgery) or on the day prior to surgery.
13. Week 4 and 8 calls as appropriate based on surgery date.
14. Premenopausal study participants who did not have a period between surgery and Visit 2 will receive a follow-up phone call to assess LMP. This follow-up call will be made 14-21 days after expected period date, or 28-35 days after study visit 2 if no expected period date is known.

## 7.2 Baseline Testing/Prestudy Evaluation (Screening Visit 1)

### 7.2.1 Pre-Study procedures include:

- Informed Consent
- Medical History (from surgical consultation note)
- Record Concomitant Medications and any baseline symptoms
- Physical Exam including vitals Record Breast Cup Size
- Verification by surgeon that radiology review does not reveal clinical or radiologic findings suspicious for invasive disease on the ipsilateral side.
- Clinical Labs – including CBC and Chemistry Panel must be completed within 14 days of randomization. Clinical labs may be run as rush tests with results reported same day or within 24 hours.
- Premenopausal women are those who have had the last menstrual period (LMP) within the last 12 months. Premenopausal women with child-bearing potential are those with at least one ovary, an intact uterus, and LMP less than 12 months previously. Premenopausal women who have undergone bilateral tubal ligation are not considered to be of child-bearing potential.

- For Premenopausal women, record last menstrual period and estimated next menstrual period dates. One week after estimated next menstrual period date, call participant to confirm and record actual menstrual period date.
- Pregnancy Test (only offered for premenopausal women with child-bearing potential).
- Blood collection for research purposes
  - Two 2.7mL blue top tubes (Citrate) to obtain plasma for Coagulation panel.
  - Two 10 mL lavender top tubes (K2EDTA) to obtain plasma and buffy coat (WBCs for DNA/RNA isolation) for the following purposes:
    - a) Plasma for measuring hormones (estradiol, progesterone).
    - b) Plasma for measuring IGF-1, IGFBP-3, and SHBG.
    - c) Buffy coat will be saved for DNA/RNA isolation.
- BESS questionnaire (Appendix C)
- Drug administration instruction and practice

7.2.2 Subjects will be instructed to keep a study diary to document their use of study medication (Appendix B). They will be offered the use of a phone app instead of a study diary. If they do not possess a smart phone, one will be provided for the duration of the study, and will be returned at the end. If not returned, the cost of the phone (\$100) will be deducted from the final study compensation payment.

7.2.3 Patients will be randomized when the baseline clinical lab results have been reported and both eligibility and appropriate stratification have been confirmed. Baseline testing and procedures must have been completed within 14 days of randomization. Once the participant has been randomized (within 90 days of DCNB), the participant's study drugs will be given/shipped to her overnight. Patients must begin study agents within 5 days of randomization. Patients will be given/sent 2 canisters of 4-OHT or placebo gel and 1 bottle of 120 tamoxifen or placebo capsules per bottle. Once the participant has been randomized, study team will begin the process of requesting paraffin blocks of core biopsy or sections of the paraffin block, from institutions that do not allow release of paraffin block.

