## SCHEMA

### Phase IIB pre-surgical trial of oral tamoxifen (TAM) versus transdermal 4-hydroxytamoxifen (4-OHT) in women with DCIS of the breast.

1 Baseline Assessment: Medical history, physical exam, medication review, pregnancy test (for pre-menopausal women of child-bearing potential), review of last menstrual period, clinical lab blood draw, research blood draw, request for core biopsy block or sections and core, and BESS questionnaire.

2 Phone Calls: Medication, compliance, and toxicity review

3 Week 4 and 8 calls as appropriate based on surgery date

4 Pre-Surgical Assessment: Medical history, physical exam, medication review, pregnancy test (for pre-menopausal women of child-bearing potential), review of last menstrual period, clinical lab blood draw, research blood draw, tissue collection, and BESS questionnaire.

5 Up to 108 eligible patients will be enrolled and no more than 100 subjects will start intervention after being randomized.

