## **4.2 Exclusion Criteria**

4.2.1 Exogenous sex steroid use within 4 weeks prior to diagnostic core needle biopsy (DCNB). Use of vaginally administered estrogens and hormone coated IUD such as Mirena is permitted and use should continue until surgery.

4.2.2 History of any prior ipsilateral breast radiotherapy. Previous unilateral radiation of the contralateral side is allowed.

4.2.3 History of other prior breast cancer-specific therapy within the previous 2 years (chemotherapy, anti-HER2 agents, endocrine agents, everolimus, CDK4-6 inhibitors).

4.2.4 Skin lesions on the breast that disrupt the stratum corneum (eg eczema, ulceration).

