### **7.4 Evaluation at Completion of Study Intervention**

#### Study Visit 1: Day of Surgery (following 4-10 weeks of study agent)

- Physical Exam including vitals. The source document for this may be anesthesia or surgery H&P, completed within 14 days prior to surgery.
- BESS questionnaire\*
- Toxicity and AE Assessment\*
- Record Concomitant Medications\*
- Collection of agent and compliance check\* - Capsule count and study gel application
- Clinical Labs – including CBC and Chemistry Panel
- Blood collection for research purposes:

- Two 2.7 mL Blue Top tube (citrate) to obtain plasma for coagulation panel.
- Two 10mL Lavender top tubes (K2EDTA) to obtain plasma and buffy coat or white blood cells (WBCs) for following purposes:
  - a) Plasma for measuring tamoxifen and its metabolites [tamoxifen, *N*-desmethyl tamoxifen, (*E*) 4-OHT, (*Z*) 4-OHT, (*E*) endoxifen, and (*Z*) endoxifen].
  - b) Plasma for measuring steroid hormones (estradiol, progesterone).
  - c) Plasma for measuring IGF-1, IGFBP-3, and SHBG.
  - d) Buffy coat will be saved for DNA/RNA isolation.
- Collection of surgical specimen for drug concentration assay – see section 10 for details.
- Pregnancy Test (only offered for premenopausal women with child-bearing potential).
- Recording of depth of lesion from skin, based on wire localization films in subjects undergoing breast conserving surgery, or on direct measurement during grossing of mastectomy slices in subjects undergoing mastectomy.
- For Premenopausal women, record last menstrual period and estimated next menstrual period dates. Confirm and record actual menstrual period date at Visit 2 or the final phone call.

\*BESS Questionnaire, toxicity and AE assessment, review of concomitant medications, and compliance check (collection and review of study agent) may be performed at either Visit 1 (day of surgery) or on the day prior to surgery.

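### The pregnancy-test rule in Section 7.2.1 requires a period within 12 months, so some eligible women who could be pregnant are not tested

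*Combined protocol and SAP*

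**What the plan says.** Section 7.2.1 gives the only menopausal criterion in the protocol: "Premenopausal women are those who have had the last menstrual period (LMP) within the last 12 months". The next sentence defines the group to be tested: "Premenopausal women with child-bearing potential are those with at least one ovary, an intact uterus, and LMP less than 12 months previously". Women with a bilateral tubal ligation are then taken out of that group.

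The test is tied to this definition in three places:
- The schema lists, at baseline and before surgery, a "pregnancy test (for pre-menopausal women of child-bearing potential").
- Section 7.2.1 restricts the screening test in the same way.
- Section 7.4 words the day-of-surgery item as "Pregnancy Test (only offered for premenopausal women with child-bearing potential").

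Footnote 3 of the schedule of events leaves out the menopausal qualifier: "Pregnancy tests will be performed on all women with child-bearing potential". It gives no definition of its own.

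Three eligibility rules matter here. Section 4.2.1 allows a hormonal IUD and wants it kept in place until surgery. Section 4.2.13 excludes pregnant women and expects that some participants will be nursing mothers, who are to stop breastfeeding. Section 4.1.5 describes tamoxifen as teratogenic and requires contraception from heterosexually active women who could conceive, with no condition on the date of the last period.

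**The concern.** A last period 12 months ago or more is a fair sign of menopause only when nothing else explains the absence of bleeding. Section 7.2.1 does not ask for the reason. A woman may have working ovaries and a uterus and still not bleed because of an IUD that the protocol permits, an endometrial ablation, or a recent pregnancy followed by breastfeeding. Under the written rule she has no child-bearing potential, so neither scheduled test is offered to her.

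What is at stake is detecting an existing pregnancy before 4 to 10 weeks of study drug. Half of the women randomized receive oral tamoxifen, and Section 4.1.5 states that the fetal effects of the gel are unknown. For the women in this gap, the pregnancy exclusion in 4.2.13 has no scheduled test behind it.

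**Working it through.** The plan gives no figure on this point, so the check applies the written rule to the kinds of women the eligibility criteria admit.

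**Notation.** O = at least one ovary; U = uterus present; T = bilateral tubal ligation; L = last period less than 12 months ago; C = absence of periods has a cause other than menopause.

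**Rule as written (7.2.1, schema, 7.4).** Test if O and U and L and not T.

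**Rule proposed below.** Test if O and U and not T, unless there have been no menses for at least 12 months with no other cause. That is: O and U and not T and (L or C).

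**Difference.** The proposed rule contains the written one, so no woman loses a test. The women added are exactly those with O, U, C, not T and not L.

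| Woman (no tubal ligation) | As written | Proposed |
|---|---|---|
| Ovary, uterus, period within 12 months | tested | tested |
| Hormonal IUD, ovary, uterus, no period for 12 months or more | not tested | tested |
| Endometrial ablation, ovary, uterus, no period for 12 months or more | not tested | tested |
| Recent pregnancy or lactation, no period for 12 months or more | not tested | tested |
| Hysterectomy, ovaries kept | not tested | not tested (no uterus) |
| Both ovaries removed | not tested | not tested |
| No period for 12 months or more, no other cause | not tested | not tested |

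**Are the three added groups eligible?** The IUD group is admitted expressly by 4.2.1. The ablation group is not mentioned, and no criterion excludes it. The postpartum group is foreseen by 4.2.13. Counting a full-term pregnancy as 40 weeks from the last period, a woman whose periods have not returned passes the 12-month limit about 12 weeks after delivery (40 + 12 = 52 weeks).

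**Does other text supply a different test criterion?** Footnote 3 relies on a term defined only in 7.2.1. Section 3.7 mentions a determination of menopause and a pregnancy test where needed, and states no criterion for either. Section 7.2.3 asks that stratification be confirmed before randomization and also gives no criterion.

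**Primary analysis.** Menopausal status is also a randomization stratum (13.2) and a covariate in the primary model (13.4.3), so the effect of mislabelling was simulated. From 13.4.2: 80 evaluable women, SD 5.4, correlation 0.5, margin 2.6, one-sided alpha 0.10. Assumed, because the documents do not give them: 40% premenopausal, with menopausal effects of 2 points on baseline Ki-67 and 1.5 points on post-treatment Ki-67. There were 40,000 runs per setting; simulation SE of the type I error = sqrt(0.1 × 0.9 / 40000) = 0.0015.

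| Premenopausal women mislabelled | Type I error at the margin | Power at no true difference |
|---|---|---|
| 0% | 0.0994 | 0.878 |
| 5% | 0.1017 | 0.873 |
| 15% | 0.1005 | 0.878 |
| 30% | 0.1016 | 0.880 |

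The primary test does not change materially even when 30% are mislabelled.

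**The case against.** The strongest defence is that other safeguards cover these women. Section 4.1.5 requires contraception whatever the date of the last period, and 4.2.13 excludes pregnancy. The one route the protocol expressly admits, the hormonal IUD, is itself accepted contraception and stays in until surgery. This stands and is why the point is minor. It does not close the gap: contraception from enrolment does not detect a pregnancy that already exists, and an exclusion without a test depends on the woman knowing she is pregnant. The IUD argument also does not reach the ablation and postpartum groups.

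A second defence is that 7.2.1 defines a qualified term, premenopausal women with child-bearing potential, while footnote 3 covers all women with child-bearing potential and so may be wider. That reading is possible. The schema and 7.4 repeat the narrower term, however, and no section defines the wider one, so a coordinator has only 7.2.1 to apply.

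A third is that some routes are remote. Section 4.2.1 bars "Exogenous sex steroid use within 4 weeks prior to diagnostic core needle biopsy (DCNB"), so a woman whose periods were suppressed by another hormonal contraceptive would need to have stopped before that window and not bled since. That is fair, and the point does not rely on this case.

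A reader might also infer that these women enter the wrong randomization stratum and that this undermines the primary result. The documents do not support that. The label is set before randomization and in the same way in both arms, and the simulation shows no material effect. Postmenopausal is undefined, so placing these women there by default is itself an inference. At most the covariate and the exploratory subgroup in 13.5.4 are slightly blurred. Redefining the stratum by cause of amenorrhoea would need an age limit that the documents do not give, and would replace a simple rule applied alike at seven sites with a case-by-case judgement.

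**Conclusion.** The point holds as a minor gap in pregnancy testing. Applied as written, 7.2.1 withholds both scheduled tests from eligible women who have a uterus and an ovary, no bilateral tubal ligation, and 12 months or more of amenorrhoea from a cause other than menopause.

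The documents do not say how many women this covers. The number is probably small in a population with screen-detected DCIS, and no prevalence is claimed. The conclusion assumes that sites follow the written rule; a site that tests on clinical judgement would already close the gap.

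Two stronger conclusions should not be drawn. The sections do not contradict one another, because footnote 3 can be read consistently with 7.2.1. Nor are these women unprotected, given 4.1.5 and 4.2.13. Sample size, alpha, the primary model and the randomized comparison are not in question.

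**What to change.** Use one rule in 7.2.1, the schema, footnote 3 of the schedule and 7.4: offer the baseline and day-of-surgery pregnancy test to any woman with a uterus, at least one ovary and no bilateral tubal ligation, unless she has had no menses for at least 12 months with no other cause. Give examples of other causes: hormonal IUD, endometrial ablation, recent pregnancy or lactation.

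Without an age limit, an older woman whose bleeding stopped with an ablation years ago would also be tested. The clinical team may therefore add an upper age above which no test is needed. The rule can be adopted before that age is chosen.

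The stratum definition can stay as it is. At most, add that a woman with a bilateral oophorectomy counts as postmenopausal for the stratum and the subgroup, since under the present wording she is premenopausal if her last period was within 12 months.

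The cost is one CRF field for the cause of absent bleeding and a few extra tests of a kind already in the schedule. No visit, assay or analysis is added.
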